9.4.2 Multivariate display of immunogenicity endpoints

Data visualization techniques may be used to explore the relationship among immunogenicity readouts across assays, and across readouts for assays that produce high dimensional data. The set of readouts may be based on one of the primary endpoints (e.g., neutralizing Abs), on the set of primary endpoints, or on immunogenicity endpoints that also include secondary or exploratory endpoints. To understand the relationship between pairs of readouts, scatter plots may be used when the number of readouts is small or for a larger number of readouts, a heatmap showing the degree of correlation between any two pairs. Principal component analysis (PCA) and associated ‘biplots’ of the scores and loadings are particularly useful to understand associations between readouts, especially when readouts are correlated [10]. PCA is a method to reduce the dimensionality of the number of readouts to a smaller set of values (principal components) that are normalized linear combinations of the readouts in such a way that the first principal component accounts for the most variability in the data and subsequent components, while maximizing variability, are uncorrelated with each other. A ‘biplot’ displays the first and second principal component scores and principal component loadings. The x-axis is the value from the first principal component and the y-axis is the second principal component, where each axis label includes the percentage of variation in the total set of readouts captured by the principal component. The top axis is the first principal component loadings and the right axis is the second principal component loadings. An arrow is drawn for each immunogenicity readout (e.g., Env-specific CD4+ T cell polyfunctionality score) from the origin to the point defined by its first two principal component loadings. The length of the arrow represents the amount of total variation of the set of readouts captured by the given readout. The direction of

an arrow conveys the extent to which the variation of a readout is in the direction of the first or second principal component. The angle between two arrows conveys information about the correlation of the two readouts, with a zero degree angle denoting perfect correlation and a 90 degree angle denoting no correlation. Each arrow on the biplot is labeled by the immunogenicity readout it represents. A biplot is annotated with key meta-information such as the treatment arm (most common application) or a demographic category. Depending on the application, K-means clustering and hierarchical clustering may also be applied for multivariate graphical display of immunogenicity readouts.

9.4.3 Primary analyses of neutralization data

The primary measure of antibody neutralization is the response to the response to the vaccine-matched BG505.T332N isolate. As well, responses to a single highly neutralization-sensitive Tier 1 virus (MW965.26) will be assessed. The mean magnitude of the response to the vaccine-matched isolate will be estimated for each arm and compared to the pooled placebo group. As well, the ratio of the response to the vaccine-matched antigen, relative to that to the neutralization-sensitive isolate, will be estimated for each arm.

If a Tier 2 panel of viral isolates is used to assess the breadth of neutralizing antibody responses, the area-under-the-magnitude-breadth curve (AUC-MB) to a global panel of viral isolates [11] will be computed for each participant with evaluable neutralization data, as described in [12]. 95% CIs about the four differences in mean AUC-MB for each vaccine regimen versus the pooled placebo groups (vaccine – placebo), will be calculated.

9.4.4 Analysis of CD4+ T cell responses as measured by the ICS assay

The analysis of CD4+ T cell response rates as measured by the ICS assay will be evaluated and compared as described under the general approach. For each T cell subset, the positivity call for each peptide pool will include a multiple comparison adjustment for the number of peptide pools used in the assay. In general, the Mixture Models for Single-cell Assays (MIMOSA) statistical framework [13] and/or the Fisher's exact test-based positivity criteria will be used. The magnitude of marginal response will be analyzed as described for quantitative data in the general approach section. For each T-cell subset, graphs will be used to display the background-subtracted magnitudes for each participant by protein, treatment arm and timepoint. When 3 or more cytokines are being measured by the ICS assay, the polyfunctionality of ICS responses may also be analyzed as an exploratory endpoint. Besides descriptive plots of the magnitude of polyfunctional responses, the COMPASS (Combinatorial Polyfunctionality analysis of Antigen-Specific T-cell Subsets) statistical framework [14] may also be used to perform joint modelling of multiple T-cell subsets of different cytokine combinations. For example, the functionality score (FS) and the polyfunctionality score (PFS) may be used to summarize the multi-parameter ICS responses.

9.4.5 Analysis of epitope mapping data

The minimal set of optimal length epitopes that can explain the observed T cells responses to a set of individually tested overlapping 15-mer peptides may be obtained to assess the breadth and depth of the T cell responses based on the epitope mapping data.

When human leukocyte antigen (HLA) data are also available, computational HLA:peptide binding predictors (e.g., NetMHCpan) may be used to more accurately identify each participant's T cell epitopes.

The set of epitopes may also be used to assess "coverage" of a representative set of circulating viruses by each participant's set of T-cell responses. The coverage provided by each epitope is defined by the fraction of viruses that match the sequence of the mapped epitope. The coverage provided by a participant's set of epitopes is defined by the fraction of viruses covered by at least one of the participant's epitopes.

9.4.6 Analysis of multiplexed immunoassay data

When a small panel of analytes (e.g. ≤ 5) is being assessed in a multiplexed immunoassay, the analysis of response rates and response magnitudes will be evaluated and compared under the general approach. When a larger panel is being assessed, 3 approaches may be considered to evaluate the magnitude and breadth of these responses. First, Magnitude–Breadth (M-B) curves may be employed to display individual- and group-level response breadth as a function of magnitude. Applied to Tier 2 virus neutralizing antibody data, response breadth is defined as the number of isolates with magnitude above a positivity threshold. Two choices are to compare the M-B curves among vaccine arms, as follows: a non-parametric Wilcoxon rank sum test on the subject-specific AUC-MB or a Kolmogorov-Smirnov type test on the 2 group-average M-B curves. Simulations can be used to obtain 2-sided p-values for the latter test. Second, a weighted-average score-like variable may be constructed to account for the correlations between analytes as an integrate magnitude of responses to multiple analytes. Similar group comparison methods described in the first approach may be adopted. Third, machine-learning approaches such as super-learning [15] will be employed which achieve the goal of reducing the dimensionality of the assay readouts and simultaneously identifying individual responses and groups of responses that differ between treatment groups or over time.

9.5 Analyses and data sharing prior to end of scheduled follow-up visits

Any analyses conducted prior to the end of the scheduled follow-up visits should not compromise the integrity of the trial in terms of participant retention or safety or immunogenicity endpoint assessments. In particular, early unblinded analyses by treatment assignment require careful consideration and should be made available on a need to know basis only. Interim blinded safety and immunogenicity data should not be shared outside of the SMB, HVTN 137 PSRT, the protocol team leadership, the HVTN Executive Management Team, the study product developer, and the study sponsor and/or its designee(s) for their regulatory reporting unless approved by the protocol leadership and the HVTN leadership.

9.5.1 Safety analyses

During the course of the trial, unblinded analyses of safety data will be prepared approximately every 4 months during the main study for review by the SMB. Ad hoc safety reports may also be prepared for SMB review at the request of the HVTN 137 PSRT.

9.5.2 Immunogenicity analyses

An unblinded statistical analysis by treatment assignment of a primary immunogenicity endpoint may be performed when all participants have completed the corresponding primary immunogenicity visit and data are available for analysis from at least 80% of these participants. Similarly, an unblinded statistical analysis by treatment assignment of a secondary or exploratory immunogenicity endpoint may be performed when all participants have completed the corresponding immunogenicity visit and data are available for analysis from at least 80% of these participants. However, such analyses for a secondary or exploratory immunogenicity endpoint will only take place after the primary immunogenicity endpoint (neutralizing antibody response) reaches the aforementioned threshold. The Laboratory Center will review the analysis report prior to distribution to the protocol chairs, DAIDS, study product developer, and other key HVTN members and investigators. Reports for distribution or presentation should use PubIDs and not participant ID (PTIDs) for individual responses. Distribution of reports will be limited to those with a need to know for the purpose of informing future trial-related decisions. The HVTN leadership must approve any other requests for HVTN immunogenicity analyses prior to the end of the scheduled follow-up visits.

10. SAFETY TABLES AND FIGURES

10.1 List of Tables

SMB reports and Safety FSRs include the following tables.

- Enrollment Report
- Demographics and Study Product Administration Frequencies
- Overall Protocol Status
- Maximum Local Reactogenicity Summary
- Maximum Systemic Reactogenicity Summary
- Adverse Events by Body System and Severity – By Decreasing Frequency
- Adverse Events by Preferred Term and Severity – By Decreasing Frequency – Includes Severe, Life-Threatening or Death Events Only
- Adverse Events by Preferred Term and Severity – By Decreasing Frequency – Includes All Severities
- Adverse Events by Preferred Term and Severity – By Decreasing Frequency – Includes Related Events Only
- Adverse Events by Preferred Term and Relationship to Study Product – By Decreasing Frequency – Includes Events of Any Relationship
- Expedited Adverse Experiences (EAEs) Reported to the Regulatory Support Center (RSC) Listing
- Adverse Events of Special Interest (AESI) Listing
- Medically Attended Adverse Events (MAAE) Listing
- Pregnancy Listing
- HIV Infection Results from Lab and Reported by Site Listing
- Study Product Administration Errors Listing

Safety FSRs include the following additional tables.

- Social Impact Summary
- Local Lab Value Summary Statistics
- Listing of Adverse Events by Treatment Arm, Participant, and Onset Date
- End of Study Diagnostic ELISA Testing Results Listing
- Local Laboratory Values Meeting Grade 1 AE Criteria or Above Listing

10.2 Participant Listings

The following listings of participant-level data are included in SMB reports only.

- Discontinuations
- Severe or Life-Threatening Local Reactogenicities

- Severe or Life-Threatening Systemic Reactogenicities
- Moderate, Severe or Life-Threatening Erythema and Induration
- Severe, Life-Threatening, or Fatal Adverse Events
- Related Adverse Events

10.3 List of Graphs

SMB reports and Safety FSRs include the following graphs.

- Maximum Local Reactogenicities
- Maximum Systemic Reactogenicities
- Boxplots for hemoglobin, platelets, WBC, neutrophils, lymphocytes, ALT, and creatinine at baseline and each post-vaccination follow-up visit

11. ASSAY-SPECIFIC TABLES AND FIGURES FOR PROTOCOL TEAM REPORTS

11.1 Intracellular Cytokine Staining (ICS)

HIV-1-specific CD4+ and CD8+ T-cell responses will be measured by intracellular cytokine staining as previously described (De Rosa, 2012 & Horton, 2007). CD4+ and CD8+ T cells expressing IFN- γ and/or IL-2 as well as CD4+ T cells expressing IFN- γ and/or IL-2 and/or CD154 will be analyzed. A validated 27-color panel (experiment assay ID 117, analysis plan 051 for Part A and experiment assay ID 123, analysis plan 059 for Part B) will be used to evaluate BG505 gp41 and BG505 gp120 at the following visits:

- Part A: visit 6 (Month 0.5; 2 weeks post 1st vaccination), visit 9 (Month 2.5; 2 weeks post 2nd vaccination), and possibly visit 14 (Month 8).
- Part A with optional second boost: visit 6 (Month 0.5; 2 weeks post 1st vaccination), visit 9 (Month 2.5; 2 weeks post 2nd vaccination), visit 13 (Month 6.5), and possibly visits 15 (Month 12) and 16 (Month 18).
- Parts B and C: visit 9 (Month 2.5; 2 weeks post 2nd vaccination), visit 13 (Month 6.5), and possibly visits 15 (Month 12) and 16 (Month 18).

Several criteria are used to determine if data from an assay are acceptable and can be statistically analyzed. The blood draw date must have been within the allowable visit window as determined by the protocol. Post-infection samples from HIV-infected participants are excluded. After sample thawing and overnight incubation, the viability of the PBMC must have been 66% or greater for testing to have proceeded. If it is not, a new specimen for that participant at that time point will be thawed for testing. If the PBMC viability of the second thawed aliquot is below this threshold, the ICS assay will not be performed and no data will be reported to the statistical center for the participant-time point. For the negative control acceptance criteria in Part A only, if the average cytokine response for the negative control wells is above 0.1% for either the CD4+ or CD8+ T cells, the sample will be retested. If the retested results are above 0.1%, the data will be excluded from analysis; otherwise, the retest data will be used.

The total numbers of CD4+ and CD8+ T cells must also have exceeded certain thresholds. If the number of CD4+ T cells is < 10,000 or the number of CD8+ T cells is < 5,000 for any of the HIV-1 peptide pools or for one of the negative control replicates for a particular sample, data for that stimulation will be filtered. If both negative control replicates fail for number of T cells, the sample will be retested. If one negative control replicate fails for number of T cells, the negative control replicate with sufficient cells will be used.

Response magnitudes of CD4+ and CD8+ T cells to Total Env will be calculated as the sum of BG505 gp41 and BG505 gp120. Responder to Any Env will be taken as the maximum response of BG505 gp41 and BG505 gp120. All pools are included regardless of positive or negative responder status, and negative magnitudes are not censored at 0.

To assess positivity for a peptide pool within a T-cell subset, a two-by-two contingency table will be constructed comparing the HIV-1 peptide stimulated and negative control data. The four entries in each table are the number of cells positive for IFN- γ and/or IL-2 and the number of cells negative for IFN- γ and/or IL-2 for both the stimulated and the negative control data. If both negative control replicates are included, then the average number of total cells and the average number of positive cells are used. A one-sided Fisher's exact test is applied to the table, testing whether the number of cytokine-producing cells for the stimulated data is equal to that for the negative control data. Since multiple individual tests (for each peptide pool) are conducted simultaneously, a multiplicity adjustment will be made to the individual peptide pool p-values using the Bonferroni-Holm adjustment method. If the adjusted p-value for a peptide pool is ≤ 0.00001 , the response to the peptide pool for the T-cell subset is considered positive. Because the sample sizes (i.e., total cell counts for the T-cell subset) are large, e.g., as high as 100,000 cells, the Fisher's exact test has high power to reject the null hypothesis for very small differences. Therefore, the adjusted p-value significance threshold is chosen stringently (≤ 0.00001). If at least one peptide pool for a specific HIV-1 protein is positive, then the overall response to the protein is considered positive. If any peptide pool is positive for a T-cell subset, then the overall response for that T-cell subset is considered positive. Data from the placebo groups in Part A (P1 and P2) and Part B (P3, P4, P5, and P6) will be pooled as Group C1 and Group C2 respectively.

Naïve (N), Central Memory (CM), Effector Memory (EM), and Terminally Differentiated (TEMRA) memory cell subsets will be analyzed in the final report as a percent of CD4 and CD8 T-cells, as well as a relative percent of cytokine-expressing IFN- γ and/or IL-2 subsets for positive responders only. Relative percentages of each memory cell subset within a participant will sum to 100%.

11.1.1 List of Tables

- Response rate table by T cell subset, antigen, cytokine, visit number (visit month), and treatment group.
- Summary statistics (minimum, 25th percentile, median, 75th percentile, maximum, mean, standard deviation) among all participants, by T cell subset, antigen, cytokine, visit number (visit month), and treatment group.
- Summary statistics (minimum, 25th percentile, median, 75th percentile, maximum, mean, standard deviation) among positive responders by T cell subset, antigen, cytokine, visit number (visit month), and treatment group. Table of comparison of response rates between treatment groups by isotype, antigen, and visit among positive responders.
- Table of comparison of response magnitudes between treatment groups by isotype, antigen, and visit among all responders.

11.1.2 List of Graphs

- Boxplots of background-subtracted percent of cells expressing IFN- γ and/or IL-2 by T cell subset, antigen, cytokine, visit number (visit month), and treatment group.
- Spaghetti plots of background-subtracted percent of cells expressing IFN- γ and/or IL-2 over time, by T cell subset, antigen, cytokine, and treatment group.
- Spaghetti plots of background-subtracted percent of T cells expressing naïve and memory cell subsets, by T cell subset, memory cell subset, and treatment group (4 rows of memory cell subsets per page).
- Spaghetti plots of relative percent of naïve and memory cell subsets out of positive T cells expressing IFN- γ and/or IL-2, by T cell subset, memory cell subset, and treatment group (4 rows of memory cell subsets per page).
- Reverse CDFs of background-subtracted percent of cells expressing IFN- γ and/or IL-2 by T cell subset, antigen, cytokine, and treatment group.
- Scatterplot of background-subtracted percent of cells expressing IFN- γ and/or IL-2 at Month 2.5 vs. prime interval, by T cell subset, antigen for Part A
- Scatterplot of background-subtracted percent of cells expressing IFN- γ and/or IL-2 at Month 6.5 vs. prime interval, by T cell subset, antigen for Part A
- Scatterplot of background-subtracted percent of cells expressing IFN- γ and/or IL-2 at Month 6.5 vs. boost interval, by T cell subset, antigen

11.2 B-Cell Phenotyping (BCP)

HIV-1 Env-specific B cells induced by vaccination will be identified and characterized using fluorescently-labelled recombinant Env proteins (BG505-SOSIP.664 and BG505-SOSIP.S241N) in combination with a flow cytometry antibody panel at the following visits:

- Part A: visit 2 (baseline, pre vaccination), visit 6 (Month 0.5; 2 weeks post 1st vaccination), visit 9 (Month 2.5; 2 weeks post 2nd vaccination), and possibly visit 14 (Month 8).
- Part A with optional second boost: visit 6 (Month 0.5; 2 weeks post 1st vaccination), visit 9 (Month 2.5; 2 weeks post 2nd vaccination), visit 13 (Month 6.5), and possibly visits 15 (Month 12) and 16 (Month 18).
- Parts B and C: visit 2 (baseline pre vaccination), visit 9 (Month 2.5; 2 weeks post 2nd vaccination), visit 13 (Month 6.5), and possibly visits 15 (Month 12) and 16 (Month 18).

Live total B cells are identified using doublet exclusion, lymphocyte scatter profile, viability dye, and the following lineage markers: negative for CD3, CD56 and CD14, and positive for CD19 and CD20. IgG+ B cells are further gated on IgD negative and IgG+.

All data reported are the raw frequencies with no background or baseline subtraction or adjustments and are listed below:

- The % BG505-SOSIP.664+ of total B cells equals the frequency of double-positive BG505-SOSIP.664 gp140+ B cells out of total B cells.
- The % BG505-SOSIP.S241N+ of total B cells equals the frequency of double-positive BG505-SOSIP.664 gp140+ B cells that are negative for the BG505-SOSIP.664 mutant (BG505-SOSIP.S241N) out of total B cells. (Part A only)
- The % BG505-SOSIP.664+ of IgG+ B cells equals the frequency of double-positive BG505-SOSIP.664 gp140+ IgG+ B cells out of IgG+ B cells.
- The % BG505-SOSIP.S241N+ of IgG+ B cells equals the frequency of double-positive BG505-SOSIP.664 gp140+ IgG+ B cells that are negative for the BG505-SOSIP.664 mutant (BG505-SOSIP.S241N) out of IgG+ B cells. (Part A only)
- The % BG505-SOSIP.664+ IgG+ of total B cells equals the frequency of double-positive BG505-SOSIP.664 gp140+ IgG+ B cells out of total B cells. (Part B only)
- The % BG505-SOSIP.664+ IgG+ of memory B cells equals the frequency of double-positive BG505-SOSIP.664 gp140+ IgG+ B cells out of memory B cells. (Part B only)
- The % BG505-SOSIP.664+ IgM+ of total B cells equals the frequency of double-positive BG505-SOSIP.664 gp140+ IgM+ B cells out of total B cells. (Part B only)
- The % BG505-SOSIP.664+ IgM+ of memory B cells equals the frequency of double-positive BG505-SOSIP.664 gp140+ IgM+ B cells out of memory B cells. (Part B only)
- The % BG505-SOSIP.664+ IgM+ IgD+ of total B cells equals the frequency of double-positive BG505-SOSIP.664 gp140+ IgM+ IgD+ B cells out of total B cells. (Part B only)
- The % BG505-SOSIP.664+ IgA+ of total B cells equals the frequency of double-positive BG505-SOSIP.664 gp140+ IgA+ B cells out of total B cells. (Part B only)
- The % BG505-SOSIP.664+ IgA+ of memory B cells equals the frequency of double-positive BG505-SOSIP.664 gp140+ IgA+ B cells out of memory B cells. (Part B only)

- The % Plasmablasts of B cells equals the frequency of plasmablast cells out of B cells. (Part B only)
- The % BG505-SOSIP.664+ plasmablast cells of total plasmablasts equals the frequency of double-positive BG505-SOSIP.664 gp140+ plasmablast cells out of total plasmablast cells. (Part B only)

To assess positivity for the detection of SOSIP.664 gp140+ and BG505-SOSIP.S241N gp140+ B cells, Fisher's exact test will be used: A two-by-two contingency table is constructed comparing the post-vaccination and baseline (visit 2) data. The four entries in each table were the numbers of Env-specific B cells and non-Env-specific B cells after vaccination and at baseline. A one-sided Fisher's exact test is applied to the table, testing whether the number of Env-specific B cells for the post-vaccination data is equal to that for the data from baseline, versus an alternative hypothesis that it is greater. Because the sample sizes (i.e., total cell counts for the B-cell subset) are large, e.g., as high as 100,000 cells, the Fisher's exact test has high power to reject the null hypothesis for very small differences. Therefore, the p-value significant threshold is chosen stringently (≤ 0.00001). Data from the placebo groups in Part A (P1 and P2), Part B (P3, P4, P5, and P6), and Part C (P7 and P8) will be pooled as Group C1, Group C2, and Group C3 respectively.

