The difference between arms at a specific timepoint will be tested with a nonparametric Wilcoxon rank sum test if the data are not normally distributed and with a 2-sample t-test if the data appear to be normally distributed. Individual tests comparing the 6 pairs of vaccine arms will be performed unless prespecified. If rank-based tests are used, then the tests will be inverted to construct Hodges-Lehmann point estimates and 2-sided $(1 - 0.05/6) \times 100\%$ confidence intervals (CIs) about the differences in location centers of the 6 pair-wise comparisons of vaccine arms. If actual-value tests are used then the Dunnett's procedure will be used to construct simultaneous confidence intervals about the pairs of mean differences for the many-to-one comparisons [2] when multiple vaccine arms are each compared with the pooled placebo group. Given that all pair-wise comparisons between the multiple vaccine arms are of interest, the Tukey procedure [3] will be used. An appropriate data transformation (e.g., \log_{10} transformation) may be applied to better

satisfy assumptions of symmetry and homoscedasticity (constant variance). Significance of the differences between pairs will be evaluated using two procedures, first based on whether the simultaneous 95% CIs exclude zero and secondly based on whether the nominal (unadjusted) 95% CIs exclude zero.

Scatterplots will be used to visualize the association between quantitative immune responses at Month 2.5 and prime interval, and between quantitative immune responses at Month 6.5 and both prime and boost interval variables in Part A.

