11.2.1 List of Tables

- Response rate table by B cell subset, visit number (visit month), and treatment group.
- Summary statistics (minimum, 25th percentile, median, 75th percentile, maximum, mean, standard deviation) among all participants, by B cell subset, visit number (visit month), and treatment group.
- Summary statistics (minimum, 25th percentile, median, 75th percentile, maximum, mean, standard deviation) among positive responders by B cell subset, visit number (visit month), and treatment group.
- Table of comparison of Env-specific B cells response rates between treatment groups by B cell subset and visit
- Table of comparison of Env-specific B cell response magnitudes between treatment groups by B cell subset and visit among all responders and positive responders only.

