11.4 Binding Antibody Multiplex Assay (BAMA)

Serum HIV-1-specific total binding IgG antibody responses will be measured at the 1:50 dilution against the gp41 and BG505 SOSIP.664 AviB antigens on samples collected from Part A and Part B's participants at week 0 (visit 2 – baseline), week 10 (visit 9 – 2 weeks post 2nd vaccination), and if applicable, week 26 (visit 13 – 2 weeks post optional 2nd boost or 3rd vaccination), week 32 (visit 14), week 52 (visit 15), and week 78 (visit 16). Data from the placebo groups in Part A (P1 and P2) and Part B (P3, P4, P5, P6) will be pooled as Group C1 and Group C2 respectively.

BAMA testing for Part C will include the Trimer 4571 antigen and will be performed on all available participant serum samples collected from Part C study arm groups 7 and 8 at visits 2 (month 0, baseline), 9 (month 2.5, 2 weeks post second vaccination), 13 (month 6.5, 2 weeks post third vaccination), 15 (month 12, 6 months post third vaccination), and 16 (month 18, 12 months post third vaccination).

The assay readout is from a Bio-Plex instrument (Bio-Rad). The Bioplex software provides 2 readouts: a background-subtracted mean fluorescent intensity (MFI), where background refers to a plate level control (i.e., a blank well run on each plate), and a concentration based on a standard curve. Net MFI (MFI*) is MFI minus Neg, where 'Neg' refers to a sample-specific background measure. Samples from post-enrollment visits are declared to have positive responses if they meet three conditions: (1) the MFI* values are greater than or equal to the antigen-specific cutoff (based on the 95th percentile of the baseline visit serum samples and at least 100 MFI), (2) the MFI* values are greater than 3 times the baseline (day 0) MFI* values, and (3) the MFI values

are greater than 3 times the baseline MFI values. Net MFI is used to summarize the magnitude at a given time-point. If sufficient immunogenicity is observed, samples may be titrated to calculate antibody titers (AUC), in which case geometric mean titers between treatment groups at each time point will be compared using two-sample T-test comparing the means of log AUC.

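### B-cell and BAMA magnitudes are compared between arms without the baseline value already collected; the tests are valid, but precision may be given up, depending on a correlation the SAP does not state

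*SAP*

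**What the plan says.** **B-cell phenotyping (SAP 11.2, 11.2.1).** The reported magnitudes are unadjusted: "All data reported are the raw frequencies with no background or baseline subtraction or adjustments and are listed below". The planned output includes a "Table of comparison of Env-specific B cell response magnitudes between treatment groups by B cell subset and visit". Baseline is assayed in Part B: "Parts B and C: visit 2 (baseline pre vaccination), visit 9 (Month 2.5; 2 weeks post 2nd vaccination), visit 13 (Month 6.5". It also decides who is a responder: "A two-by-two contingency table is constructed comparing the post-vaccination and baseline (visit 2) data".

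**BAMA (SAP 11.4).** Week 0 (visit 2) sera are tested. For magnitude, "Net MFI is used to summarize the magnitude at a given time-point"; this net value removes a sample-specific background, not the day-0 value. If samples are titrated, "geometric mean titers between treatment groups at each time point will be compared using two-sample T-test comparing the means of log AUC". One condition for a positive response is that "the MFI* values are greater than 3 times the baseline (day 0) MFI* values".

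**General rule (SAP 9.4.1).** "The difference between arms at a specific timepoint will be tested with a nonparametric Wilcoxon rank sum test if the data are not normally distributed"; otherwise a two-sample t-test is used. No covariate is named.

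**Other places where baseline information could enter (SAP 9.4.1).**
- Models with baseline predictors apply when more than 20% of participants have missing values.
- Repeated-measures models are planned in general terms.
- A semiparametric efficient method is planned for endpoints measured only in a subset.

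None of these puts the participant's own baseline into the routine single-timepoint B-cell or BAMA comparison, and no reason is given for leaving it out.

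**The concern.** The plan treats the visit 2 value as informative enough to decide whether a participant responded, but does not use it when comparing the size of the response between arms. If antigen-binding B cells or background binding IgG before vaccination predict the later value, that between-person variation stays in the error term of each of the six pairwise adjuvant contrasts.

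Arms are small: the SAP expects 18 analysable vaccinees per Part B arm at Months 2.5 and 6.5, and 17 at Months 12 and 18. What is at stake is the width of the intervals and the power for the magnitude parts of Part B secondary endpoints 2 (binding antibody) and 3 (B cells). Validity is not in question.

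**Working it through.** **Inputs from the SAP (section 8.3, Table 6).** One-sided 0.025 Wilcoxon test, normal data, SD 1 in both arms, n = 18 or 17 per arm, stated power at 1.0 SD 81% and 78%.

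**Assumption.** rho, the correlation between baseline and post-vaccination values on the analysis scale, is not in the SAP. The range 0 to 0.7 is shown.

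**Step 1: reproduce Table 6.** Simulating the stated Wilcoxon test (20,000 runs) gives 80.0% at n = 18 and 77.9% at n = 17 for 1.0 SD. Table 6 therefore describes the unadjusted test correctly.

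**Step 2: choose the comparator.** Under normality a t-test is slightly more powerful than the Wilcoxon test, so covariate-adjusted power should be set against the unadjusted t-test. Its noncentrality is d × sqrt(n/2) = 1.0 × sqrt(9) = 3.0 with 2n − 2 = 34 df, giving 83.0%. At n = 17 it is 80.7%.

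**Step 3: add baseline as a covariate.** The residual SD becomes sqrt(1 − rho²), the df become 2n − 3, and estimating the slope costs a factor 1 + 1/(2n − 4). The noncentrality is d × sqrt(n/2) / [sqrt(1 − rho²) × sqrt(1 + 1/(2n − 4))]. For n = 18 and rho = 0.5 this is 3.0 / (0.866 × 1.0155) = 3.41.

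| rho | Variance removed (rho²) | n equivalent, 18/(1 − rho²) | Power, n = 18, 1.0 SD | Change from 83.0% (points) | Power, n = 17, 1.0 SD |
|---|---|---|---|---|---|
| 0 | 0% | 18.0 | 81.8% | −1.2 | 79.3% |
| 0.2 | 4% | 18.8 | 83.3% | +0.3 | 80.9% |
| 0.3 | 9% | 19.8 | 85.2% | +2.2 | 83.0% |
| 0.5 | 25% | 24.0 | 91.2% | +8.2 | 89.4% |
| 0.7 | 49% | 35.3 | 98.0% | +15.0 | 97.3% |

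At 0.8 SD and n = 18, the unadjusted t-test has 64.5% and the adjusted test 75.5% at rho 0.5.

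**Step 4: baselines at the assay floor.** Simulation (4,000 runs per cell, n = 18, 1.0 SD; Monte Carlo SE of each power about sqrt(0.83 × 0.17/4000) = 0.6 points), unadjusted t-test to covariate-adjusted:
- 90% of baselines at the floor: 82.5% to 83.3% (underlying rho 0.5) and 82.7% to 86.2% (underlying rho 0.7), so about 1 and 4 points.
- 50% at the floor: 83.2% to 89.3% and 83.1% to 94.7%, so about 6 and 12 points.

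**Step 5: covariate or subtraction.** A change score has SD sqrt(2(1 − rho)), which exceeds 1 whenever rho < 0.5. At rho 0.2 it is 1.26, and the normal-approximation power at n = 18 and 1.0 SD falls from 85% on the post-vaccination value to 66%.

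**The case against.** The strongest reply is that nothing is wrong. An unadjusted Wilcoxon or t-test between randomized arms is valid, chance baseline imbalance is already allowed for in its type I error, and Table 6 powers that very test. This stands.

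It can also be said that no loss has been shown. Participants are HIV-uninfected, so Env-specific baselines may lie near the floor with little spread. That is an inference, not a statement in the SAP, but it is plausible, and Step 4 shows the gain could then be negligible. This too stands, although it need not hold for every readout: Part B also reports IgM+ and IgM+IgD+ antigen-binding cells, and the BAMA rule sets a threefold rise over a participant's own baseline.

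Three stronger readings are tempting but not supported:
- **A loss of ten points or more against Table 6.** Comparing 91% at rho 0.5 with the tabulated 81% mixes in the difference between t-test and Wilcoxon, and takes for granted a correlation the SAP does not give.
- **Baseline should be subtracted, because ICABA and luciferase ADCC do so.** Subtraction loses power when rho is below 0.5.
- **Adjustment cannot introduce bias anywhere.** That rests on randomization, so it covers the all-participant Part B comparisons only. The responder-only tables condition on a status defined after vaccination. The Part C versus Part B comparisons are not between arms randomized together.

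**Conclusion.** The routine between-arm magnitude comparisons for B-cell phenotyping and BAMA leave out a baseline value that is collected and already used for the responder call. This is an efficiency point, not a bias and not an error in any stated figure.

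Its size depends on rho. Against the unadjusted t-test at 1.0 SD and 18 per arm, adjustment costs about 1 point at rho 0, gains about 2 at rho 0.3, and becomes material at about 0.5 and above (8 points at 0.5, 15 at 0.7). These figures assume normal data on the analysis scale, equal SDs and the same readout at both times. For BAMA AUC the available baseline is net MFI, a proxy, so the gain may be smaller. A reader might infer that precision is certainly being lost; the SAP supports only that it may be.

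**What to change.** Add to SAP 11.2 and 11.4, for the all-participant comparisons among the randomized Part B arms, a prespecified and labelled baseline-adjusted analysis beside the present test:

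- Regress the log10 post-vaccination value on arm and log10 baseline value, with a stated floor for zeros. Use rank ANCOVA if residuals are clearly non-normal.
- Enter baseline as a covariate; do not subtract it.
- Use the same readout at baseline where it exists. For BAMA AUC, name baseline net MFI as the proxy.
- State how a missing baseline is handled, for example by mean imputation of the covariate.
- Claim no protection from bias for the responder-only or Part C versus Part B comparisons.
- In 11.2.1, make clear that the broader comparison covers all participants; it now reads as all responders, set beside positive responders only.

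The existing tests, raw-frequency displays and pairwise intervals stay as they are. The SAP is already at version 8.0, so date the addition and mark it as post hoc for any readout already analysed by arm.

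The cost is one degree of freedom per comparison, the missing-baseline rule and a little more analysis work; no new samples are needed. If simultaneous intervals are wanted for the adjusted contrasts, they must be specified too. If the team prefers not to adjust, one sentence saying why baseline is left out would close the point.
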